- Lupus Low Disease Activity State (LLDAS):^{23,24} LLDAS is defined as follows: (1) SLEDAI-2K ≤ 4 , with no activity in major organ systems (renal, central nervous system, cardiopulmonary, vasculitis, fever) and no hemolytic anemia or gastrointestinal activity (measured as maintaining a D or E score in the BILAG Gastrointestinal Body System); (2) no new lupus disease activity compared with the previous assessment measured as no new or worsening individual BILAG parameters; (3) Physician's Global Assessment of Disease Activity ≤ 1 ; (4) a current prednisolone (or equivalent) dose ≤ 7.5 mg daily; and (5) well-tolerated standard maintenance doses of immunosuppressive drugs and approved biological agents.

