6.0 Study Variables

6.1 Efficacy Assessments

The following efficacy procedures or tools will be used to assess subjects' SLE disease activity during the study:

British Isles Lupus Assessment Group (BILAG)-2004

The BILAG-2004 grades are based on recording disease activity for 97 items in 9 different organ systems (constitutional, mucocutaneous, neuropsychiatric, musculoskeletal, cardiorespiratory, gastrointestinal, ophthalmic, renal, and hematological, see Appendix 10 of the study protocol). Each item is measured qualitatively by clinical observation (yes/no, not present/improving/same/worse/new) based on lupus activity over the past 4 weeks compared with the previous 4 weeks or quantitatively by measuring hematologic and renal lab values. For abnormal lab values, the item is noted as SLE related or not SLE related. Based on scores of the 97 items, an alphabetical grade is derived for each organ system representing 5 levels of disease with A being the highest level of disease activity. The grades are given a numerical score equivalent:

- A (very active) = 12
- B (moderate disease activity) = 8
- C (mild stable disease) = 1
- D (no current disease activity but the system had previously been affected) = 0
- E (no current or previous disease activity) = 0

A global BILAG-2004 score (range from 0 to 108) is derived by summing-up the numerical score equivalents for each organ system. Grades are assigned by central reviewers based on BILAG-2004 Index Scoring along with grading conventions. The detailed grading conventions are documented in the Central Review Plan including the handling of missing data when assigning the grades. Grades assigned in 'BILAG Grading' eCRF page will be used for analysis purpose.

SLEDAI-2K

The SLEDAI-2K is a global index based on weighted scores for each of 24 clinical findings rated as present or absent at the time of the visit or in the last 30 days (see Appendix 11 of the Study Protocol). The total score for SLEDAI-2K ranges from 0 to 105 with higher scores representing higher disease activity. The total score collected in 'SLEDAI-2K' eCRF page will be used for analyses. The detailed grading conventions are documented in the Central Review Plan including the handling of missing data when assigning the grades.

Cutaneous Lupus Erythematosus Disease Area and Severity Index (CLASI)

Sponsor: Bristol-Myers Squibb
Protocol no: IM011021

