- SLEDAI-2K ≤ 4
 - The following items on the SLEDAI-2K are scored as 'no': seizure, psychosis, organic brain syndrome, visual disturbance, cranial nerve disorder, lupus headache, CVA (cerebrovascular accident), vasculitis, urinary casts, hematuria, proteinuria, pyuria, pleurisy, pericarditis, and fever
 - No hemolytic anemia on BILAG (item 96 on BILAG)
 - All BILAG gastrointestinal items scored as 0 (all items under gastrointestinal organ system graded D or E)
- No new lupus disease activity compared with the previous assessment measured as no new or worsening individual BILAG parameter

This definition will be implemented as follows:

- None of the 97 BILAG items are scored 4 (=worse) or 5 (=new)
- None of the 97 BILAG items are newly marked abnormal SLE related

Sponsor: Bristol-Myers Squibb
Protocol no: IM011021

If an item is rated Abnormal SLE Related at a visit then it must have been rated Abnormal SLE related at the previous visit.

- Physician's Global Assessment of Disease Activity ≤ 1
- Prednisone or equivalent dose ≤ 7.5 mg/day
- Well tolerated standard maintenance doses of immunosuppressive drugs and approved biologic agents

Similar analyses will be conducted as for the primary endpoint, including the primary analysis and sensitivity analysis.

11.7.2.5 Tender and Swollen Joint Count at Week 48

The change from baseline in counts for tender, swollen, and tender + swollen (active) joints will be calculated on all subjects in the randomized population.

- Tender 40-joint count at Week 48 – tender 40-joint count at baseline
- Swollen 40-joint count at Week 48 – swollen 40-joint count at baseline
- Tender + swollen (active) 40-joint count at Week 48 - tender + swollen 40-joint count at baseline

[figure not shown]

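### The SAP's Week 48 LLDAS rule tests blood-count, creatinine and GFR items only for becoming newly abnormal, so worsening of an already flagged item does not disqualify a responder

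*SAP*

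**What the plan says.** Protocol 8.1 defines the second LLDAS criterion as "no new lupus disease activity compared with the previous assessment measured as no new or worsening individual BILAG parameters". SAP 6.2 repeats it, and SAP 11.7.2.4 opens its implementation with the same two-part condition, "no new or worsening individual BILAG parameter".

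The SAP then turns the criterion into two tests:

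- Test 1: "None of the 97 BILAG items are scored 4 (=worse) or 5 (=new" (closing bracket omitted).
- Test 2: "None of the 97 BILAG items are newly marked abnormal SLE related", explained as "If an item is rated Abnormal SLE Related at a visit then it must have been rated Abnormal SLE related at the previous visit".

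SAP 6.1 says how BILAG items are recorded. Some are assessed by clinical observation, as yes/no or on the scale running from not present to new. Others are assessed "or quantitatively by measuring hematologic and renal lab values". For the latter it adds: "For abnormal lab values, the item is noted as SLE related or not SLE related". Protocol Appendix 10 agrees. Haemoglobin, white cells, neutrophils, lymphocytes and platelets (items 90 to 94) are printed as values, and creatinine and GFR (items 86 and 87) are printed with units of measurement.

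LLDAS at Week 48 is a secondary endpoint (protocol Table 4). The protocol's summary of changes and SAP 5.4.1 place the Week 48 endpoints in the multiplicity-controlled hierarchy.

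**The concern.** The criterion has two limbs, new and worsening. For items recorded as values, the written implementation covers only the first. A programmer who follows SAP 11.7.2.4 exactly would count as a responder a patient whose SLE-related blood count was already abnormal at Week 44 and is clearly worse at Week 48. The criterion being implemented would exclude that patient.

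At stake is whether the reported Week 48 LLDAS rate is the rate of the state that the protocol defines. The primary endpoint, SRI(4) at Week 32, does not use this rule.

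**Working it through.** The plan states no figure on this point, so there is none to reproduce. The check sets the criterion against the rule and then runs the rule on test cases.

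**Step 1. Criterion against tests.**

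| Item, previous visit to Week 48 | Criterion 2 | Test 1 | Test 2 |
|---|---|---|---|
| Rated item, now scored worse or new | fails | fails | not needed |
| Value item, normal, then abnormal and SLE related | fails (new) | no score to act on | fails |
| Value item, flagged at both visits, now further from normal | fails (worsening) | no score to act on | passes |

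The third row is the gap. Test 2 compares flags and does not compare values.

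**Step 2. Which items.** Appendix 10 has 12 items recorded as values: 78, 79, 82, 83, 84, 86, 87 and 90 to 94. Items 78 and 79 are blood pressure and are not laboratory values. Items 82 to 84 are urine protein or albumin and are largely covered because SLEDAI-2K proteinuria must be absent. That leaves 12 − 2 − 3 = 7: items 86, 87 and 90 to 94. The gap is clearest for the five haematology items.

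**Step 3. Do the other LLDAS conditions close it?**

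- SAP 11.7.2.4 requires 15 of the 24 SLEDAI-2K items to be absent. The list ends "urinary casts, hematuria, proteinuria, pyuria, pleurisy, pericarditis, and fever". Its laboratory items are the four urinary ones. Thrombocytopenia and leukopenia are not on it.
- In Appendix 11 those two items weigh 1 point each, whatever the depth. Platelets of 95, 60 and 30 x10^9/L each give 1 point. Thrombocytopenia 1 + leukopenia 1 + low complement 2 = 4, which still meets the limit of 4.
- Haemoglobin, neutrophils, lymphocytes, creatinine and GFR are not SLEDAI-2K items and add 0.
- BILAG item 96 blocks haemolysis only.
- PGA at or below 1 and prednisone at or below 7.5 mg/day are absolute limits and do not test for change.

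**Step 4. The rule applied literally to assumed patients.** All have PGA 0.8 and prednisone 5 mg/day, meet the remaining conditions and have no nonresponder event.

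| Case | SLEDAI-2K | Result |
|---|---|---|
| Platelets 95 to 60 x10^9/L, flagged at both visits | 1 | responder |
| As above, plus leukopenia (white cells flagged at both visits) and low complement | 4 | responder |
| Platelets 95 to 60 x10^9/L, flag new at Week 48 | 1 | nonresponder |

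The fall is (95 − 60)/95 = 36.8% in each case. Only the earlier flag changes the outcome.

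**Step 5. Can such patients be in the trial?** Protocol 5.2 excludes platelets below 50 x10^9/L and white cells below 1.2 x10^9/L. Appendix 11 scores thrombocytopenia below 100 and leukopenia below 3.0 x10^9/L. Patients between those limits can enter with an abnormal count.

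**Step 6. Direction.** Adding a disqualifying test can only remove responders, so each arm's rate as written is at or above the rate with the test. If the test would remove a fraction a of an active arm and p of placebo, the difference from placebo changes by −(a − p). The documents give neither a nor p, so the sign and size of that change are unknown.

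**The case against.** **The eCRF is not visible.** Test 1 speaks of all 97 items, and SAP 6.1 does not say that the SLE-related flag is the only thing recorded for a laboratory item. The SAP is to be read with the CRF (SAP 3.0). If the CRF also rates laboratory items worse or new, test 1 catches the worsening and the gap closes. This stands as a condition on the finding. Nothing in SAP 6.1 or Appendix 10 describes such a rating, and test 2 would then have little left to do.

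**The sponsor did consider worsening.** SAP 5.4.2 item 1c reads a new BILAG grade, for LLDAS, as one that has worsened since the previous assessment. That supports the intent, but 11.7.2.4 contains no comparison of haematological or renal grades. A redacted appendix or the Central Review Plan might add something, but no visible text sends this test to either.

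**Worsening of a number has to be defined somehow.** Neither document defines it for a laboratory value, and a flag rule is prespecified and reproducible. That is fair, and it is why the fix should not invent item-by-item thresholds. It does not make the flag rule an implementation of the worsening limb.

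**Stronger readings that the documents do not support:**

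- A reader might infer that the rule favours active treatment. The same rule applies to every arm, and Step 6 shows that the effect on the difference is undetermined.
- A reader might take 7 of 97 items as the size of the problem. It counts lines on a form, some of them overlapping, and is not an effect size.
- A reader might infer that the code numbers (4 and 5 in the SAP, 3 and 4 in Appendix 10, for worse and new) cause misclassification. The SAP labels its codes, and the eCRF codelist decides the matter. It is a documentation check on which this point does not rest.

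**Conclusion.** The point holds for the SAP as written. For items recorded as values, most clearly haematology items 90 to 94 and also creatinine and GFR, criterion 2 is applied only through a newly raised flag. Worsening of an item already flagged at the previous visit is not tested, so a Week 48 LLDAS responder can conflict with the criterion.

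Each arm's LLDAS rate is affected upward or not at all. How many patients are affected cannot be derived. PGA, the steroid limit and the nonresponder rules may remove some of them. No bias between arms and no effect on type I error is shown.

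The conclusion rests on one assumption: that the eCRF records these items as SAP 6.1 describes, with no worse/new rating. It should be settled before unblinding because the endpoint is in the controlled hierarchy and the repair is small.

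**What to change.** Check the eCRF first. If it already rates items 86, 87 and 90 to 94 as worse or new, cite that codelist in 11.7.2.4, and the point is closed.

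Otherwise make two changes before unblinding:

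1. Add to 11.7.2.4 that a subject is not an LLDAS responder if the centrally assigned haematological or renal BILAG grade is worse than at the previous assessment. The order can be taken from the numerical equivalents in SAP 6.1 (A 12, B 8, C 1, D and E 0), with a higher score counting as worse. This agrees with SAP 5.4.2 item 1c and needs no new thresholds.
2. Report by arm the number of Week 48 LLDAS responders whose already flagged SLE-related laboratory value moved further from normal since the previous visit. An organ grade can miss worsening within a grade. The grading conventions are in the Central Review Plan, so the documents do not show whether the fall in Step 4 would change the grade.

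As a documentation check, reconcile the worse/new code numbers in the SAP and Appendix 10 with the eCRF.

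The cost is a few lines of SAP text and one small derivation. BILAG, haematology and chemistry are already collected at Weeks 44 and 48 (protocol Table 3), so no new data are needed. The downside is possibly slightly lower LLDAS rates.

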11.7.4 Subgroup Analysis

[figure not shown]
Subgroup analyses will be performed for the primary endpoint, SRI(4) response at Week 32. Due to the reduced sample size within subgroup, no model-based adjusted odds ratios will be calculated. These analyses will include point estimates for response rate with asymptotic confidence intervals and the estimated unadjusted difference between study drug and placebo groups with Newcombe 95% confidence limits. P-values will not be reported for subgroup analyses. The following subgroups will be considered:

- Baseline CS dose (< 10 mg/day, ≥ 10 mg/day)
- Baseline SLEDAI-2K Score (< 10 , ≥ 10)
- Geographic region (North America, South America, Japan, rest of world)
- Country
- Gender (male, female)
- Age group (18 - <45 , 45 - <65 , ≥ 65 years)
- Weight ($<$ median weight, \geq median weight)
- BMI (≤ 30 kg/m², > 30 kg/m²)
- Race
- Ethnicity (Hispanic or Latino, not Hispanic or Latino)
- CS Use at baseline (yes, no)
- Anti-malarial Use at baseline (yes, no)
- Immunosuppressant Use at baseline (yes, no)
- Interferon (IFN) status (high, low)
- Years since initial diagnosis (<3 yrs, 3-6 yrs, >6 years)

[figure not shown]
Sponsor: Bristol-Myers Squibb

Protocol no: IM011021

[figure not shown]
Sponsor: Bristol-Myers Squibb

Protocol no: IM011021

[figure not shown]
Sponsor: Bristol-Myers Squibb

Protocol no: IM011021

[figure not shown]

Sponsor: Bristol-Myers Squibb

Protocol no: IM011021

Sponsor: Bristol-Myers Squibb
Protocol no: IM011021

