2 INTRODUCTION

Systemic lupus erythematosus (SLE) is a chronic progressive immune-mediated disease characterized by pleiotropic organ/tissue involvement and clinical manifestations that are varied and widespread. The most commonly affected body systems are mucocutaneous, musculoskeletal, and renal. Progression of the disease is marked by flares requiring therapy modification, and uncontrolled SLE leads to end organ damage and death. SLE prevalence in the United States is estimated at 20 to 150 cases per 100,000, and incidence is estimated at 1 to 25 per 100,000. Women are more frequently affected than men (9:1), as are people of African American and African Caribbean descent, and peak incidence occurs around the third or fourth decade of life. Autoantibodies that define the autoimmune nature of SLE have been identified. However, these autoantibodies are not specific to SLE. This and the variable clinical manifestations of SLE contribute to the complexity of diagnosis and treatment.

Current therapies are unsatisfactory, and include immunosuppressive drugs and corticosteroids (CS), which can temporarily control SLE flares and disease progression. However, the utility of these therapies wanes over time, and their use is associated with substantial undesirable effects that may outweigh any short-term improvements. One goal in the management of SLE is to achieve disease and symptom control while minimizing CS exposure. Treatments include antimalarials, immunosuppressants, biologics including belimumab, and other agents (prescribed off-label). There remains an unmet need for novel, well-tolerated, orally administered therapies that can effectively modify the disease course and control symptoms.

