5.1 Sample Size Considerations

Approximately 360 subjects are to be randomized into 1 of 4 treatment groups in a 1:1:1:1 ratio, resulting in around 90 subjects per group.

With a sample size of 90 subjects per arm, there will be at least 84% power to detect a treatment difference of 20% in SRI(4) response rates between the BID BMS-986165 treatment arms and placebo.

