The number and percentage of subjects achieving NRI-imputed SRI(4) response at Week 32 and those who do not will be reported by treatment group with the estimated response rate and asymptotic 95% confidence intervals (CIs). Differences in response rates between each active treatment group and placebo with corresponding 2-sided 95% CIs based on the continuity-corrected Newcombe method will also be provided.

Tipping Point Analysis

Tipping point analysis will further be used to assess the robustness of the primary study results. Different number of events between treatment groups will be assessed until the study conclusion is

Sponsor: Bristol-Myers Squibb
Protocol no: IM011021

changed. Each imputed value is initially imputed as a responder. The imputed values in the placebo group will remain as responders while the BMS-986165 imputed values are replaced as a non-responders one at a time, therefore changing the number of events between groups. Once all imputed values in the BMS-986165 group have been replaced with non-responders values, the data will reset to where the BMS-986165 group imputed values are all responders and one by one the imputed values in the placebo group are replaced with a non-responder until all placebo are non-responders and all BMS-986165 are responders. Furthermore, every pair of imputations between the placebo and BMS-986165 groups will be assessed similarly, creating a matrix of possible patterns.

At each iteration, the statistical analysis is assessed, and the direction of the analysis is recorded. A graph will be provided to identify at what point to which the difference in events cause a direction shift in study results. The tipping point analyses will be based on a two-sample chi-square test approach rather than a stratified CMH test approach for simplicity of the analysis.

Sensitivity analysis #1 (Treatment Policy Strategy)

The primary analysis for the primary endpoint will be repeated using a treatment policy estimand approach (Intention-To-Treat (ITT) principle). For this approach, subjects will only be imputed as non-responders if there is a missing value for the endpoint at the considered timepoint.

Sensitivity analysis #2

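### SAP 11.7.4 gives subgroup response rates asymptotic intervals, which if Wald fall short of 95% coverage in small cells; name a Wilson or exact interval (minor)

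*SAP*

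**What the plan says.** SAP 11.7.4 analyses the primary endpoint, SRI(4) response at Week 32, within subgroups. For each arm's rate: "These analyses will include point estimates for response rate with asymptotic confidence intervals". For the comparison it specifies "the estimated unadjusted difference between study drug and placebo groups with Newcombe 95% confidence limits". No score or exact method is named for the single proportion, and no minimum cell size is set for showing an interval.

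The section recognises that cells will be small: "Due to the reduced sample size within subgroup, no model-based adjusted odds ratios will be calculated". It also withholds p-values for subgroups. The factors include sex, country, race, region with Japan as its own level, and "Age group (18 - <45 , 45 - <65 , ≥ 65 years").

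SAP 5.1 plans 360 subjects in four arms, "resulting in around 90 subjects per group". SAP 11.7.1 uses the same wording for the overall rate, "with the estimated response rate and asymptotic 95% confidence intervals (CIs"), and the two-sided 95% level is explicit there: "Differences in response rates between each active treatment group and placebo with corresponding 2-sided 95% CIs".

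**The concern.** An asymptotic interval for one proportion, set beside a named score-based method for the difference, is most naturally read as Wald: the observed rate plus or minus 1.96 estimated standard errors. In small samples that interval is too short on average, and at 0/n or n/n the estimated standard error is zero, so it shrinks to a point.

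SAP 11.7.4 adapts to small cells in two places, by dropping the model and by using Newcombe limits, but leaves a large-sample interval on the single-arm rates. With no subgroup p-values and no model-based estimates, intervals are the only measure of precision in these tables. In a very small cell the reader could see nominal 95% limits that cover well below 95%, or a degenerate interval where there is least information.

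**Working it through.** The plan states no subgroup size, interval width or coverage, so there is no figure of its own to reproduce on this point.

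**Inputs**
- About 90 subjects per arm (SAP 5.1); two-sided 95% level, z = 1.96 (SAP 11.7.1).
- Cell sizes: assumed. The protocol introduction says "Women are more frequently affected than men (9:1"). If enrolment mirrors that, men per arm = 360 × 0.1 / 4 = 9. Sizes of 3–5 for small country, race or age ≥65 cells are an assumed range.
- True response rate: 30–60%, assumed, because the visible text gives no placebo rate.

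**Formulas**
- Wald: p̂ ± 1.96 √(p̂(1 − p̂)/n).
- Exact coverage at true rate p: the sum of the binomial probabilities of those counts x whose interval contains p.
- Chance of zero width: pⁿ + (1 − p)ⁿ.
- Wilson upper limit at 0/n: z²/(n + z²), with z² = 3.84.

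**Three cases by hand**
- n=3. The Wald limits are 0 to 0 for x=0, −0.20 to 0.87 for x=1, 0.13 to 1.20 for x=2, and 1 to 1 for x=3. A true rate of 0.30 is covered only by x=1 and x=2: 1 − 0.3³ − 0.7³ = 1 − 0.027 − 0.343 = 63%. At 0.50 it is 1 − 0.125 − 0.125 = 75%.
- n=5, true rate 0.30. Only x=1, 2 and 3 cover: 0.360 + 0.309 + 0.132 = 80%.
- n=9, true rate 0.32. The x=1 interval stops at 0.316 and the x=6 interval starts at 0.359, so only x=2 to 5 cover: 0.248 + 0.272 + 0.192 + 0.090 = 80%.

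**Enumeration over true rates 0.30–0.60**

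| n per arm | Wald min / mean / max | Wilson min / mean | Chance of zero width (Wald) |
|---|---|---|---|
| 3 | 63.0 / 71.9 / 75.0% | 91.8 / 96.7% | 25–37% |
| 5 | 80.1 / 86.4 / 93.8% | 92.7 / 95.5% | 6–17% |
| 9 | 80.2 / 89.1 / 93.5% | 91.2 / 94.9% | 0.4–4.0% |
| 10 | 84.0 / 89.7 / 95.0% | 92.0 / 95.1% | 0.2–2.8% |
| 18 | 89.1 / 92.2 / 95.3% | 92.4 / 95.1% | below 0.2% |
| 45 | 91.7 / 94.0 / 95.6% | 93.5 / 95.1% | negligible |
| 90 | 93.3 / 94.5 / 95.6% | 94.0 / 95.0% | negligible |

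**Limits at zero responders**
- Wald: 0 to 0 at any n.
- Wilson: 0 to 3.84/8.84 = 43% at n=5; 0 to 3.84/12.84 = 30% at n=9.
- Clopper-Pearson: 0 to 52% at n=5; 0 to 34% at n=9.

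**If asymptotic means continuity-corrected Wald** (adding 1/(2n) to each side), the interval no longer collapses. Mean coverage over the same rates is then 72% at n=3, 90% at n=5 and 94% at n=9. The shortfall nearly disappears at n=9 but remains in the smallest cells.

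**The case against.** **The method is inferred.** Neither 11.7.4 nor 11.7.1 uses the word Wald for these intervals, and Wilson is itself a large-sample method. This stands: the text is underspecified rather than explicitly wrong, and the size of the problem depends on the reading. Either way the method should be named.

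**The cell sizes are not in the documents.** No number of countries, country enrolment or race distribution is given, and the 9:1 ratio describes the disease, not the trial. This also stands. A reader might infer that many cells will hold 3–5 per arm. The documents do not establish that, although single-digit cells are likely for some countries or races in a multiregional trial of about 90 per arm. Many of the listed factors are two-way splits, and at about 45 per arm the average loss is about 1 point.

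**The consequences are contained.** No subgroup p-values are reported, and the drug–placebo difference, which bears on whether the effect varies, already has limits built from Wilson intervals. This stands and sets the severity. It also answers the reading that the single-arm limits and the Newcombe limits cannot appear in one table: they describe different quantities, and neither invalidates the other.

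**The smallest subgroups would not generally show the tightest intervals.** A reader might infer this from the zero-width case, but Wald intervals widen as n falls unless the count is 0 or n. The narrowest non-degenerate half-width is 1.96 √((1/3)(2/3)/3) = 53 points at n=3 and 1.96 √((1/9)(8/9)/9) = 21 points at n=9. At n=90 with a 50% rate it is 1.96 √(0.25/90) = 10 points. Most small cells would look imprecise, as they should.

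**A printed 0% (0% to 0%) line is not certain.** SAP 11.0 says that, by default, no percentage is shown for a zero count, and 11.7.4 does not say whether its point estimates are exempt. The n/n case is not affected by that rule.

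**Conclusion.** The point holds as a minor one. Read as Wald, the interval in 11.7.4 gives average coverage of about 89% at 9 per arm, 86% at 5 and 72% at 3, against 95–97% for Wilson, and it degenerates at 0/n or n/n. This rests on three assumptions: that asymptotic means uncorrected Wald, that some cells hold about 10 or fewer subjects per arm, and that true rates lie between 30% and 60%.

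The documents do not support a claim that the subgroup treatment comparisons are misstated, or that the primary result is affected. Only descriptive single-arm intervals change. For the overall rates in 11.7.1, at about 90 per arm, Wald averages 94.5% and Wilson 95.0%, so nothing of substance turns on the choice there.

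**What to change.** In SAP 11.7.4, replace the word asymptotic with Wilson score intervals for response rates; Clopper-Pearson is an acceptable, more conservative alternative. State whether the SAP 11.0 rule on zero counts applies to these tables. A minimum cell size for displaying an interval could also be considered.

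A matching change in 11.7.1 is optional, for consistency only.

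The cost is a few words in the SAP and one option in the procedure call. No data, hypothesis test or sample size changes.
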